APPENDIX A – TABLES, LISTINGS, AND FIGURE SHELLS

This section presents the shells for the planned Tables, Listings and Graphs to be programmed in support of the planned analyses identified in the SAP. This section is intended to support the SAP and provides guidance on the programming specifications (shells) for the planned outputs and may be updated, independent of the SAP, with any updates appropriately documented, reviewed, and approved.

The following reporting conventions will be adopted for the presentation of study data. These conventions will enhance the review process and help to standardize the presentation with common notations.

General Reporting Conventions

- All tables and data listings will be developed in landscape orientation.
- Specialized text styles, such as bolding, italics, borders, shading, superscripted and subscripted text will not be used in tables and data listings unless they add significant value to the table, figure, or data listing.
- Only standard keyboard characters should be used in tables and data listings. Special characters, such as nonprintable control characters, printer-specific characters, or font specific characters, will not be used on a table, figure, or data listing. Hexadecimal character representations are allowed (e.g., μ , α , β).
- All titles will be centered on a page. The ICH numbering convention is to be used for all outputs.
- All footnotes will be left justified and at the bottom of a page.
- Missing values for both numeric and character variables will be presented as blanks in a table or data listing. A value of zero may be used if appropriate to identify when the frequency of a variable is not observed.
- All date values will be presented as ddmmmyyyy (e.g., 29AUG2011) format. A 4-digit year is preferred for all dates.
- If applicable, all observed time values will be presented by using a 24-hour clock HH:MM:SS format (e.g., 01:35:45 or 11:26). Seconds should only be reported if they were measured as part of the study.
- All tables and data listings will have the name of the program, the location, and a date stamp on the bottom of each output.

Population Summary Conventions

- Population sizes may be presented for each classification factor as totals in the column header as (N=xxxx), where appropriate.
- Population sizes shown with summary statistics are the samples sizes (n) of subjects with non-missing values.
- All population summaries for categorical variables will include all categories that were planned and for which the subjects may have had a response. Percentages corresponding to null categories (cells) will be suppressed, however counts and percentages of missing values may be needed.

SAP FINAL Version 2.0

- All population summaries for continuous variables will include: N, mean, SD, minimum, and maximum. Other summaries (e.g., number missing, geometric mean, median, quartiles, 95% CIs, and coefficient of variation (CV) or % CV) may be used as appropriate.
- All percentages are rounded and reported to a single decimal point (xx.x %). A percentage of 100% will be reported as 100%. No value of 0% will be reported. Any computation of percent that results in 0% is to be presented as a blank.
- Population summaries that include P-values will report the P-value to 4 decimal places with a leading zero (0.0001). All P-values reported on default output from statistical software (i.e., SAS® Software) may be reported at the default level of precision. P-values <0.0001 should be reported as <0.0001 not 0.0000.

Protocol: MDGN-NFC1-ADHD-201 Page 24 of 88

SAP FINAL Version 2.0

11.1 Standard Layout for all Tables, Listings, and Listing

The following standard layout will be applied to all Tables, Listings, and Listings in support of this study. Note that programming notes may be added if appropriate after each TLF shell. These notes are noted within brackets and will not appear on the output "{}".

Protocol: MDGN-NFC1-ADHD-201 SAP FINAL Version 2.0

11.2 Planned Table Shells

Table	Table Title	Topline
14.1.1	Disposition of Study Population by Optimized Dose and Randomized Treatment (ITT Population)	х
14.1.2	Major Protocol Deviations (ITT Population)	
14.1.3	Demographics and Baseline Characteristics by Optimized Dose and Randomized Treatment (Safety Population)	х
14.1.4	Disease Characteristics at Baseline by Optimized Dose and Randomized Treatment (Safety Population)	х
14.1.5	Summary of Prior Medications by Randomized Treatment (Safety Population)	
14.2.1.1	Analysis of Change from Baseline in ADHD-RS-5: Total Score and Subscales, by Study Visit (ITT Population)	х
14.2.1.2	Summary of Change from Baseline in ADHD-RS-5 Score and Subscales by Actual Dose and Randomized Treatment, by Study Visit (ITT Population)	
14.2.2.1	Chi-Square Analysis of CGI-I Improvement, by Study Visit (ITT Population)	х
14.2.2.2	Summary of Categorical and Continuous CGI-I Scores by Randomized Treatment Group and Study Visit (ITT Population)	х
14.2.2.3	Summary of CGI-I Improvement by Optimized Dose and Randomized Treatment, by Study Visit (ITT Population)	
14.2.3.1	Chi-Square Analysis of CGI-S Improvement, by Study Visit (ITT Population)	
14.2.3.2	Summary of Categorical and Continuous CGI-S Scores by Randomized Treatment Group and Study Visit (ITT Population)	
14.2.3.3	Summary of CGI-S Improvement by Optimized Dose and Randomized Treatment, by Study Visit (ITT Population)	
14.2.4.1	Analysis of Change from Baseline in ASHS Total Score and Factors, by Study Visit (ITT Population)	
14.2.4.2	Summary of Change from Baseline in ASHS Total Score and Factors by Randomized Treatment, by Study Visit (ITT Population)	
14.2.5.1	Analysis of Change from Baseline in SCARED Score and Factors, by Study Visit (ITT Population)	
14.2.5.2	Summary of Change from Baseline in SCARED Score and Factors by Randomized Treatment, by Study Visit (ITT Population)	
14.2.6.1	Chi-Square Analysis of Response and Remission Criteria, at End of Study (ITT Population)	х
14.3.1.1	Summary of TEAEs by Dose at Onset (Safety Population)	
14.3.1.2	Incidence of TEAEs by Dose at Onset and Randomized Treatment (Safety Population)	х
14.3.1.3	Incidence of TEAEs occurring in more than 5% of subjects by Randomized Treatment (Safety Population)	

SAP FINAL Version 2.0

14.3.1.4	Incidence of Post-Treatment AE's by Randomized Treatment (Safety Population)	
14.3.1.5	Incidence of SAE's by Randomized Treatment (Safety Population)	
14.3.1.6	Incidence of TEAEs Leading to Early Termination by Randomized Treatment (Safety Population)	
14.3.1.7	Incidence of Deaths by Randomized Treatment (Safety Population)	
14.3.1.8	Incidence of TEAEs by Relationship to Study Drug by Randomized Treatment (Safety Population)	
14.3.1.9	Incidence of TEAEs by Maximum Severity by Randomized Treatment (Safety Population)	
14.3.2	Summary of Exposure to Study Drug and Compliance by Actual Dose and Randomized Treatment (Safety Population)	
14.3.3.1	Summary of Clinical Laboratory Data: Clinical Chemistry by Randomized Treatment by Study Visit (Safety Population)	
14.3.3.2	Summary of Clinical Laboratory Data: Hematology by Randomized Treatment by Study Visit (Safety Population)	
14.3.3.3	Summary of Clinical Laboratory Data: Urinalysis by Randomized Treatment by Study Visit (Safety Population)	
14.3.3.4	Shifts from Baseline of Clinical Laboratory Data: Clinical Chemistry by Randomized Treatment (Safety Population)	
14.3.3.5	Shifts from Baseline of Clinical Laboratory Data: Hematology by Randomized Treatment (Safety Population)	
14.3.3.6	Shifts from Baseline of Clinical Laboratory Data: Urinalysis by Randomized Treatment (Safety Population)	
14.3.4.1	Summary of Vital Signs by Randomized Treatment by Study Visit (Safety Population)	
14.3.4.2	Potentially Clinically Important Vital Signs by Randomized Treatment (Safety Population)	
14.3.5.1	Incidence of Abnormal ECG Findings: based on Site Interpretations by Randomized Treatment by Study Visit (Safety Population)	
14.3.5.2	Incidence of Abnormal ECG Findings: based on Central Reading by Randomized Treatment by Study Visit (Safety Population)	
14.3.5.3	Potentially Clinically Important ECG Results by Randomized Treatment (Safety Population)	
14.3.6	Summary of C-SSRS Assessments by Randomized Treatment (Safety Population)	
14.3.7	Summary of Concomitant Medications by Randomized Treatment (Safety Population)	
14.3.8	Summary of Post-Treatment Medications by Randomized Treatment (Safety Population)	
14.3.8	Summary of Post-Treatment ineutcations by Randomized Treatment (Safety Population)	

Protocol: MDGN-NFC1-ADHD-201 SAP FINAL Version 2.0

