6 GENERAL ISSUES FOR STATISTICAL ANALYSIS

6.1 General Statistical Methodology

Data processing, tabulation of descriptive statistics, calculation of inferential statistics, and graphical representations will be performed using SAS® Software (release 9.3 or higher) for Windows, unless otherwise specified.

Continuous (quantitative) variables will be summarized using descriptive statistics including number of non-missing values, mean, standard deviation (SD), median, minimum, and maximum. Where appropriate, estimates will be presented with 95% confidence intervals (CIs).

Categorical (qualitative) variables will be summarized using the number and proportion of each possible value. In general, the denominator for the percentage calculation will be based upon the total number of subjects in the study population for the treatment group. 95% CIs of proportions may also be presented for selected endpoints where applicable. Zero-count levels of variables will not display a percentage.

The minimum and maximum will be reported with the same degree of precision (i.e., the same number of decimal places) as the raw data. Measures of location (mean and median) will be

SAP FINAL Version 2.0

reported to 1 degree of precision more than the raw data and measures of spread (standard deviation) will be reported to 2 degrees of precision more than the raw data.

All statistical tests will be conducted at the 0.05 significance level using 2-tailed tests, and P-values will be reported. Assessments done on unscheduled visits will not be summarized but will be listed.

Page 12 of 88

In general, baseline and safety tables will be completed for the Safety Population unless otherwise specified. Efficacy tables for primary and secondary endpoints will be presented for the ITT Population. However, analyses of the PP Population may be performed if warranted by the data. These potential PP tables are not present in the table index.

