- SCARED Significant School Avoidance is the summation of questions 2, 11, 17, and 36.
- SCARED Total Score is the summation of all 41 questions, each scored from 0 to 2 scale.
- C-SSRS Suicidal Ideation is an indicator of any subject who experience any one of the five suicidal ideation events at least once (Questions 4, 6, 8, 10, and 12)
- C-SSRS Suicidal Behavior is an indicator of any subject who experience any one of the suicidal behavior events at least once (Questions 22, 26, 29, 32, and 35)
- C-SSRS composite endpoint of Suicidal Ideation or Behavior is an indicator of any subject who experiences any one of the ten suicidal ideation or behavior events at least once.
- TEAE An AE is defined as treatment emergent if the first onset or worsening is after the first administration of IP (NFC-1 or placebo) and not more than 7 days after the last administration of IP
- For the tabulation of TEAE's that are related to study drug, these are defined as any TEAE which is determined by the investigator as 'possibly related' or 'related'.
- Post-Treatment AE is an AE that has started more than 7 days after last administration of IP.
- Prior medications are defined as medications or therapies initiated prior to date of first dose of IP and terminating prior to date of first dose of IP. Medications that are started prior to the date of first dose of IP and are continuing after the first dose of IP are considered to be both prior and concomitant medications
- Concomitant medication is defined as any medication a subject received concurrently with study treatment.
- Post-treatment medication is defined as any medication that has started more than 7 days after the last administration of IP.
- Compliance (Overall) = $(\sum (Individual Week Compliance) * (Time-Weight)) * 100. A subject is non-compliant if they take <math>< 80\%$ or > 120% of IP.
 - Individual Week Compliance is defined as the number of capsules taken at a particular week divided by the expected number of capsules taken at a particular week. Given that a subject will be dose optimized, the number of expected capsules will vary according to which dose the subject is currently on for each day.
 - Time-Weight is the fraction of \mathbf{x}/\mathbf{y} where \mathbf{x} is the number of days in the week the subject is expected to be on dose and \mathbf{y} is the whole treatment duration defined as first dose last dose + 1.

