Note: ADHD-RS-5 = Attention Deficit Hyperactivity Disorder Rating Scale Version 5, CGI-I = Clinical Global Impression of Improvement. Percentages are 100*n/N, where N is the number of non-missing values for corresponding treatment.

Source: Listing 16.2.5.1.1, 16.2.5.1.2, 16.2.5.2

^[1] Response is defined as: (A) a change in ADHD-RS-5 total score from baseline of 30% or more, (B) a CGI-I score of 1 (very much improved) or 2 (much improved) relative to baseline, and (C) a composite requiring both (A) and (B) to be met.

^[2] Remission is defined as: (A) ADHD-RS-5 total score of 18 or less at post-baseline visits, (B) a CGI-I score of 1, and (C) a composite of (A) and (B) to be met

^[3] P-value for comparison of the frequency of Response versus No Response between the NFC-1 and Placebo treatment. The analysis is from a Chi-Square test of association at alpha = 0.05.

Protocol: MDGN-NFC1-ADHD-201

Page 1 of x Final

Table 14.3.1.1 Summary of TEAEs by Dose at Onset Safety Population

Category	NFC-1 100mg (N=xx)	NFC-1 200mg (N=xx)	NFC-1 400mg (N=xx)	All NFC-1 (N=xx)	Placebo (N=xx)
Subjects with at least one:					
Treatment-Emergent Adverse Event	xx (xx x%)	xx (xx x%)	xx (xx.x%)	xx (xx x%)	xx (xx.x%)
TEAE Related to Study Drug [1]	xx (xx x%)	xx (xx x%)	xx (xx.x%)	xx (xx x%)	xx (xx.x%)
Serious Adverse Event	xx (xx x%)	xx (xx x%)	xx (xx.x%)	xx (xx x%)	xx (xx.x%)
TEAE Leading to Study Drug Discontinuation	xx (xx x%)	xx (xx x%)	xx (xx.x%)	xx (xx x%)	xx (xx.x%)
Adverse Event Leading to Death	xx (xx x%)	xx (xx x%)	xx (xx.x%)	xx (xx x%)	xx (xx.x%)

Note: Percentages are 100*n/N. TEAE = Treatment-Emergent Adverse Event

[1] Any AE determined by the investigator as 'possibly related' or 'related' is considered related for purposes of analysis.

Source: Listing 16.2.6.1, 16.2.6.2, 16.2.6.3, 16.2.6.4

Protocol: MDGN-NFC1-ADHD-201

Page 1 of x Final

Table 14.3.1.2
Incidence of TEAEs by Dose at Onset and Randomized Treatment
Safety Population

SOC Preferred Term [1]	NFC-1 100mg (N=xx)	NFC-1 200mg (N=xx)	NFC-1 400mg (N=xx)	NFC-1 (N=xx)	Placebo (N=xx)
Number of Subjects with at Least One AE	xx (xx x%)	xx (xx x%)	xx (xx x%)	xx (xx x%)	xx (xx x%)
<soc 1=""></soc>	xx (xx x%)	xx (xx x%)	xx (xx x%)	xx (xx x%)	xx (xx x%)
<event 1=""></event>	xx (xx x%)	xx (xx x%)	xx (xx x%)	xx (xx x%)	xx (xx x%)
<event 2=""></event>	xx (xx x%)	xx (xx x%)	xx (xx x%)	xx (xx x%)	xx (xx x%)
<event 3=""></event>	xx (xx x%)	xx (xx x%)	xx (xx x%)	xx (xx x%)	xx (xx x%)

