<soc 2=""></soc>	xx (xx x%)	xx (xx x%)	xx (xx x%)	xx (xx x%)	xx (xx x%)
<event 1=""></event>	xx (xx x%)	xx (xx x%)	xx (xx x%)	xx (xx x%)	xx (xx x%)
<event 2=""></event>	xx (xx x%)	xx (xx x%)	xx (xx x%)	xx(xxx%)	xx (xx x%)
<event 3=""></event>	xx (xx x%)	xx (xx x%)	xx (xx x%)	xx (xx x%)	xx (xx x%)
<soc 3=""></soc>	xx (xx x%)	xx (xx x%)	xx (xx x%)	xx (xx x%)	xx (xx x%)
<event 1=""></event>	xx (xx x%)	xx (xx x%)	xx (xx x%)	xx (xx x%)	xx (xx x%)
<event 2=""></event>	xx (xx x%)	xx(xxx%)	xx (xx x%)	xx (xx x%)	xx (xx x%)
<event 3=""></event>	xx (xx x%)	xx (xx x%)	xx (xx x%)	xx (xx x%)	xx (xx x%)

Note: Percentages are 100*n/N. Subjects were counted only once for each System Organ Class (SOC) or Preferred Term. TEAE is defined as AEs occurring or worsening with an onset at the time of or following the start of treatment with study medication. TEAE = Treatment-Emergent Adverse Event.

[1] Adverse Events were coded from MedDRA (version xx x).

Source: Listing 16.2.6.1

Table 14.3.1.3

Incidence of TEAEs occurring in more than 5% of subjects by Randomized Treatment

{Similar shell as Table 14.3.1.2; Source: Listing 16.2.6.1} {Update footnote to add definition of TEAE, update first row of table}

Safety Population

Table 14.3.1.4
Incidence of Post-Treatment AEs by Randomized Treatment
Safety Population

{Similar shell as Table 14.3.1.2; Source: Listing 16.2.6.1} {Update footnote to add definition of TEAE, update first row of table}

Table 14.3.1.5
Incidence of SAEs by Randomized Treatment
Safety Population

{Similar shell as Table 14.3.1.2; Source: Listing 16.2.6.2} {Update footnote to add definition of SAE, update first row of table}

Table 14.3.1.6
Incidence of TEAEs Leading to Early Termination by Randomized Treatment Safety Population

{Similar shell as Table 14.3.1.2; Source: Listing 16.2.6.3} {Update update first row of table}

Table 14.3.1.7 Incidence of Deaths by Randomized Treatment Safety Population

{Similar shell as Table 14.3.1.2; Source: Listing 16.2.6.1} {Update update first row of table}

Page 1 of x Final

Table 14.3.1.8
Incidence of TEAEs by Relationship to Study Drug by Randomized Treatment
Safety Population

Preferred Term [1]	NFC-1	Placebo
Causality	(N=xx)	(N=xx)
Number of Subjects with at least one TEAE	xx (xx.x%)	xx (xx.x%)
Potentially Related	xx (xx x%)	xx (xx.x%)
Not Related	xx (xx x%)	xx (xx.x%)
<soc 1=""></soc>	xx (xx x%)	xx (xx.x%)
Potentially Related	xx (xx x%)	xx (xx.x%)
Not Related	xx (xx x%)	xx(xx.x%)

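### TEAE tables by dose at onset show percentages with an undefined N and no time at dose, so their columns can differ for reasons unrelated to dose

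*SAP*

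**What the plan says.** The SAP's index of planned tables lists Table 14.3.1.2, "Incidence of TEAEs by Dose at Onset and Randomized Treatment (Safety Population"), and marks it topline. It is the only table in the 14.3 series so marked. Table 14.3.1.1 gives summary categories by dose at onset. Both shells have columns for 100, 200 and 400 mg NFC-1, all NFC-1 and placebo, each headed with its own N. The footnotes read "Note: Percentages are 100*n/N. TEAE = Treatment-Emergent Adverse Event" (14.3.1.1) and "Note: Percentages are 100*n/N. Subjects were counted only once for each System Organ Class (SOC) or Preferred Term" (14.3.1.2). Neither shell has a row or header line for exposure.

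Two other places touch on N. SAP 6.1 says that, in general, "the denominator for the percentage calculation will be based upon the total number of subjects in the study population for the treatment group"; SAP 8.1 uses treatment group to mean NFC-1 or placebo. The population conventions in Appendix A say "Population sizes may be presented for each classification factor as totals in the column header as (N=xxxx), where appropriate". The same three dose columns also appear in Tables 14.1.1, 14.1.3 and 14.1.4, where they are titled by optimized dose.

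On the TEAE window, SAP 6.3 includes onsets "not more than 7 days after the last administration of IP". The 14.3.1.2 footnote sets no end: "TEAE is defined as AEs occurring or worsening with an onset at the time of or following the start of treatment with study medication". Neither says which dose column takes an event that starts after the last dose.

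Time at dose is planned elsewhere. Table 14.3.2, "Summary of Exposure to Study Drug and Compliance by Actual Dose and Randomized Treatment (Safety Population"), is not topline. It has treatment duration in each dose column and cites Listing 16.2.4.1, which defines duration per dose level.

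Under Protocol 9.9 and 10.1.3.1, all subjects start at 100 mg twice daily and may move weekly. An ineffective response leads to the next strength if tolerated, and an intolerable one to a lower strength. Visit 5 is the last visit for titration. Tables 14.2.1.2 (actual dose), 14.2.2.3 and 14.2.3.3 (optimized dose) split efficacy by dose.

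**The concern.** A percentage by dose at onset depends on how long subjects were at that dose and on who is in the denominator. Here the titration scheme makes time at dose unequal by design, and the denominator is not defined. A reader of the topline package would see one percentage per dose beside placebo, with nothing to show that the placebo column covers more time, or that a different N would change which dose looks worst. A gap between columns could be taken as a dose-related safety signal, or as reassurance, when neither is present. If N is settled only after unblinding, the choice is also made with the results in view.

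The efficacy splits raise a related problem. Subjects who respond early stop at a low dose and non-responders move up, so the columns are formed by the outcome that they display. At Visit 3 nobody has yet taken more than 100 mg, yet Table 14.2.2.3 shows that visit by optimized dose.

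**Working it through.** The plan states no figure on this point, so there is none to reproduce. The check is whether the columns can differ when dose has no effect at all.

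**Longest time at each dose (nominal visit days).** Total treatment is 42 days (Protocol 10.2). Moving to 200 mg after Day 7 leaves 42 − 7 = 35 days. Moving to 400 mg after Day 14 leaves 42 − 14 = 28 days. The visit windows (± 2 days) shift these slightly.

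**Ceilings under one constant hazard.** Let q be the 42-day placebo risk; risk over d days is 1 − (1 − q)^(d/42).

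- q = 30% (assumed): 400 mg, 1 − 0.70^(28/42) = 21.2%; 200 mg, 1 − 0.70^(35/42) = 25.7%.
- q = 17/30 = 56.7% (phase 1b headache frequency, Protocol 5.2, borrowed as a 42-day risk): 42.7% and 50.2%.

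These ceilings apply when N is the arm or the ever-exposed subjects.

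**Effect of N.** Assumptions not in the documents: mean ADHD-RS-5 change by week −4, −6, −7.5, −8.5, −9.5, −10; SD 11; correlation between visits 0.6; baseline 38; acceptable response = 25% drop, then held; no optional increases; no dropout; drug inert. Simulating 400,000 subjects gives three paths:

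| Final dose | Share | Weeks at 100/200/400 mg |
|---|---|---|
| 100 mg | 0.308 | 6/0/0 |
| 200 mg | 0.171 | 1/5/0 |
| 400 mg | 0.521 | 1/1/4 |

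With q = 30%, risks over 1, 4, 5 and 6 weeks are 5.77%, 21.2%, 25.7% and 30.0%.

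- N = NFC-1 arm: 100 mg, 0.308 × 30.0 + 0.692 × 5.77 = 13.2%; 200 mg, 0.171 × 25.7 + 0.521 × 5.77 = 7.4%; 400 mg, 0.521 × 21.2 = 11.0%.
- N = ever exposed (shares 1.00, 0.692, 0.521): 13.2%, 7.4/0.692 = 10.7%, 11.0/0.521 = 21.2%.
- N = optimized to that dose: 13.2/0.308 = 43%, 7.4/0.171 = 43%, 11.0/0.521 = 21%.

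Placebo is 30% throughout and the hazard is identical at every dose.

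**Effect of timing.** Make the Week 1 hazard three times that of later weeks, keeping q = 30%, so Week 1 carries 3/8 of the cumulative hazard. With N = ever exposed:

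- 100 mg: 0.308 × 30.0 + 0.692 × (1 − 0.7^(3/8)) = 17.9%.
- 200 mg: [0.171 × (1 − 0.7^(5/8)) + 0.521 × (1 − 0.7^(1/8))]/0.692 = 8.2%.
- 400 mg: 1 − 0.7^(4/8) = 16.3%.

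Now 100 mg is highest, not 400 mg.

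**What rates would show.** The constant hazard is −ln(0.70)/6 = 0.0594 per week, or 5.9 per 100 patient-weeks in every column. For 45 subjects (Protocol 7.1), patient-weeks are 45 × 2.54 = 114, 45 × 1.38 = 62 and 45 × 2.08 = 94, giving about 7/4/6 expected events. Exact Poisson 95% intervals are roughly 2 to 13, 2 to 17 and 2 to 14 per 100 patient-weeks.

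**Efficacy split.** In the same inert-drug model, Week 6 change by final dose is −17.5/−12.9/−4.6, against −10.0 pooled. Selection alone produces the spread.

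**The case against.** Several points against the concern stand.

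- A reader might infer that the SAP has two competing rules for N. It does not. SAP 6.1 is qualified as a general rule, and the Appendix A sentence is a permissive header convention. What the text supports is that N is undefined for these columns.
- A reader might also infer that every dose will look safer than placebo, or that 400 mg will look worst. Neither is general. With N = optimized dose, two columns exceed placebo; with early-onset risk and N = ever exposed, 100 mg is highest.
- The illustration's response inputs and the 30% risk are assumed. Protocol 9.9 gives no numerical threshold for an acceptable response.
- The statement in SAP 2.1.2 that dose level will be examined belongs to the efficacy endpoints and does not bear on TEAEs. SAP 10 speaks of dose groups replacing NFC-1 versus placebo in several tables, but both TEAE shells keep an all-NFC-1 column.
- Exposure by dose is already planned in Table 14.3.2, with the per-dose-level listing as its source. What is missing is a link from the TEAE tables.
- SAP section 3 says that dosing follows response and tolerability. The efficacy splits are descriptive, without p-values, and not topline. Only their footnotes lack the caveat.
- Protocol 13.4.4 plans no formal inference for safety, and the rates would be imprecise.

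These points limit the weight of the concern. They do not supply a definition of N or put time at dose beside the topline percentages.

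**Conclusion.** The point holds in a limited form and deserves a change to the shells. Tables 14.3.1.1 and 14.3.1.2 report TEAEs by dose at onset with an undefined N and no time at dose, while the design caps time at 200 and 400 mg at 35 and 28 of 42 nominal days. With no dose effect, the 400 mg column can read 11% or 21%, and the 100 mg column 13% or 43%, depending only on N. Those sizes rest on one constant hazard, a 30% placebo risk, the assumed response model and no dropout. They show how large the distortion could be; they do not predict the trial's result. The undefined N and the unequal time do not depend on those assumptions.

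The Visit 3 split in Table 14.2.2.3 and the missing footnotes on the dose-split efficacy shells are smaller labelling faults. The all-NFC-1 columns and the randomised comparisons are unaffected.

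**What to change.** 1. In Tables 14.3.1.1 and 14.3.1.2, define N as subjects ever exposed at that dose. Show patient-weeks at each dose and for placebo in the header. Give TEAEs per 100 patient-weeks for the any-TEAE rows and for terms above 5%. State which column takes a TEAE starting within 7 days after the last dose, and keep those events and days both in or both out of the rate.
2. Optionally, since placebo is titrated through the same nominal levels, tabulate placebo by matched dose level at onset, or by study week, as a timing comparator. The matched-level columns are also formed after randomisation, so they remain descriptive.
3. Footnote the dose-split outcome tables: dose was selected on response and tolerability, so the columns are not a dose-response. In Table 14.2.2.3, label the Visit 3 split as later optimized dose, or drop it.
4. Cross-reference Table 14.3.2 from the TEAE tables.

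The cost is a little programming. Dose dates and AE onset times are already in Listings 16.2.4.1 and 16.2.6.1, and Appendix A lets shells be updated independently of the SAP. The change should be made before unblinding.

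The rates have limits that should be stated beside them. They rest on few events, and they remove unequal time at risk only, not early-onset risk or selection by tolerability. With no dose effect, varying susceptibility and tolerability-driven titration, illustrative rates still ran from 6.3/5.8/5.5 to 7.9/5.6/4.5 per 100 patient-weeks. No change to the titration rule is implied.
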